24.5. Retention of Records

Federal and local regulations require that the Investigator retain a copy of all regulatory documents and records that support the data for this study (eg, informed consents, laboratory reports, source documents, study drug dispensing records) for whichever of the following is the longest period of time:

- A period of 2 years following the final date of approval by the FDA or other regulatory agency of the study drug for the purposes that were the subject of the investigation; or
- A period of 5 years following the date on which the results of the investigation were submitted to the FDA or other regulatory agency in support of, or as part of, an application for a research or marketing permit for the study drug for the purposes that were the subject of the investigation

Endo will notify Investigators once one of the above 2 timeframes has been satisfied.

If the investigation does not result in the submission of the data in support of, or as part of, an application for a research or marketing permit, records must be retained for a period of 2 years following notification by Endo Pharmaceuticals Inc. that the entire clinical investigation (not merely the Investigator's portion) is completed, terminated, or discontinued or 2 years following withdrawal of the Investigational New Drug application (IND).

If the Investigator retires, relocates, or for other reasons withdraws from the responsibility of keeping the study records, custody must be transferred to a person who will accept the responsibility. Endo must be notified in writing of the name and address of the new custodian. Study records should not be destroyed without consultation with Endo Pharmaceuticals Inc.

24.6. Subject Confidentiality

All subject records submitted to Endo Pharmaceuticals Inc. or its designee will be identified only by initials and code number. Subjects' names are not to be transmitted to Endo Pharmaceuticals Inc. The Investigator will keep a Master Subject List on which the identification number and the full name, address, and telephone number of each subject are listed. It is the Investigators' responsibility to inform study subjects that representatives of the Sponsor, FDA, or other regulatory agencies may review all records that support their participation in the study. The Investigator will adhere to all privacy laws to which she is subject.

25. TERMINATION OF STUDY

The Sponsor has the right to suspend or terminate the study at any time. The study may be suspended or terminated for any reason.

APPENDIX A. DOCUMENTS REQUIRED PRIOR TO INITIATION OF THE STUDY

As a Sponsor of a clinical study, Endo Pharmaceuticals Inc. has an obligation to ensure that the study will be conducted by a qualified Investigator with sufficient resources of time, personnel, and physical facilities to conduct the study and to ensure that the Investigator understands and agrees to comply with the protocol, applicable regulations, policies, and procedures. The following documentation is required:

From the Principal Investigator

1. A signed agreement to perform the study per protocol (the signature page will suffice).
2. A signed Letter of Financial Agreement (including confidentiality statement).
3. Name(s) of the Principal Investigator and of all sub-Investigator(s)
4. All address(es) of the clinical site(s).
5. A current medical license valid where he/she practices and a current curriculum vitae for the Principal Investigator (signed and dated) and all sub-investigators, to contain at least the following elements:
 - a. For physicians:
 - i. Date of degree in Medicine
 - ii. Name of the Institution granting the degree in Medicine.
 - iii. Previous clinical postings with dates.
 - b. For non-physician allowed by national law or regulations to act as clinical Investigators:
 - i. Date and description of most advanced degree.
 - ii. Name of the Institution granting the degree in number (i).
 - iii. Other accreditation or qualifications relevant to the study.
 - iv. Previous postings with dates.
 - v. Name and qualification (see 5a above) of the physician or dentist in charge of study subjects.

Note: If a non-physician is serving as Principal Investigator, then a qualified physician must be assigned as a sub-Investigator for the trial, to be responsible for all trial-related medical decisions.

6. Written notification of Institutional Review Board/Independent Ethics Committee/Human Research Ethics Committee (IRB/IEC/HREC) approval. The minimum requirements are as follows:
 - a. Dated letter, including:
 - i. The date on which the meeting for the review of the study protocol took place.
 - ii. Study protocol/amendment number, and version date

[figure not shown]
- iii. A clear statement of approval of the protocol and the informed consent text with version date, and authorization for the study to proceed.
 - iv. If the Investigator or any sub-Investigator is a part of the IRB/IEC/HREC Review Board, assurance that the Investigator abstained from voting at the meeting(s) when the study was discussed.
 - b. A dated list of the members and their occupations.
 - c. A specimen copy of the Committee-approved informed consent text to be used in the study.
7. Food and Drug Administration (FDA) Form 1572 (for studies submitted under a US Investigational New Drug application [IND]).
 8. Financial Disclosure Certification or Certification of Non-Disclosure (for studies to be submitted for a US New Drug Application/Biologics License Application [NDA/BLA]).

[figure not shown]
Other

[figure not shown]
Any other documentation required by national law or regulations to be in the possession of the Sponsor or the Investigator for study participation or study initiation.

[figure not shown]
**APPENDIX B. HEXSEL DM, DAL'FORNO T, HEXSEL CL. A
VALIDATED PHOTONUMERIC CELLULITE SEVERITY
SCALE. J EUR ACAD DERMATOL VENEREOL.
2009;23(5):523-528.**

[figure not shown]
[figure not shown]

[figure not shown]

[figure not shown]
This document is a scanned copy of a printed document. No warranty is given about the accuracy of the copy. Users should refer to the original published version of the material.

bpm	Beats per minute
brpm	Breaths per minute
BUN	Blood urea nitrogen
CR-PCSS	Clinician Reported Photometric Cellulite Severity Scale
CSS	Cellulite Severity Scale
ECG	Electrocardiogram
eCRF	Electronic Case Report Form
EFP	Edematous fibrosclerotic panniculopathy
EN3835	Collagenase clostridium histolyticum
EOS	End of Study
EOT/ET	End of Treatment/Early Termination
GAIS	Global Aesthetic Improvement Scale
I-GAIS	Investigator Global Aesthetic Improvement Scale
MedDRA	Medical Dictionary for Regulatory Activities
mg	Milligram
MH	Medical history
mL	Milliliter
mmHg	Millimeters of mercury
mmol	Millimoles
PCI	Potentially clinically important/important
PR-PCSS	Patient Reported Photometric Cellulite Severity Scale

Table 1: Abbreviations (Continued)

Abbreviation	Definition
SAE	Serious adverse event
SAP	Statistical Analysis Plan
S-GAIS	Subject Global Aesthetic Improvement Scale
TEAE	Treatment-emergent adverse event
ULN	Upper limit of normal
µmol	Micromoles
WHO	World Health Organization

0. REVISION HISTORY

1. STUDY DESIGN

1.1. Description of Study Design

This clinical study is a multicenter, open-label extension study. Subjects who completed the entire double-blind, placebo-controlled, parent trial (EN3835-201) and sign an informed consent form will be eligible to participate in this study.

After the Sponsor has broken the EN3835-201 study drug blind, subjects enrolled in the open-label study will have the following options:

- To have no EN3835 treatments in study EN3835-202
- If received EN3835 in study EN3835-201, may elect to have a qualifying quadrant other than the one treated with EN3835 in study EN3835-201 (termed *re-dosing*)
- If received EN3835 in study EN3835-201 and the cellulite severity scores of the treated quadrant have returned to or are higher than EN3835-201 baseline scores, may elect to have the previously treated quadrant retreated with EN3835 (termed *re-treatment*)
- If received placebo in study EN3835-201, may elect to have a qualifying quadrant treated with EN3835; also may elect to have a second qualifying quadrant treated with EN3835 after completing the treatment course

Following completion of safety and cellulite assessments at Day 71 of the double-blind study (EN3835-201), subjects will be asked if they wish to continue in the open-label extension to the double-blind study (Screening A). Subjects enrolled in study EN3835-202 who elect to receive EN3835 treatment (either re-treatment, re-dosing, or a first treatment) must meet specific inclusion and exclusion criteria for eligibility during re-screening (Screening B) prior to EN3835 dosing.

Previously placebo-treated subjects will have the option to receive a second course of EN3835 in the same or different qualifying quadrant after at least 28 days following the end of the first treatment course (eg, the Screening B visit of second quadrant could be performed on Day 71 after treating the first quadrant). The selected quadrant can be re-treatment or re-dosing.

At each treatment course, subjects will receive 3 treatment sessions (Day 1, Day 22, and Day 43) unless the chosen quadrant has no further treatable edematous fibrosclerotic panniculopathy (EFP) dimples and the Investigator rates the quadrant a score of 0 on the Clinician Reported Photounumeric Cellulite Severity Scale (CR-PCSS). The same dimples within a quadrant or different dimples within a quadrant may be treated at each session but injections must all be within the selected quadrant for all 3 sessions. Each treatment session will be separated by approximately 21 days. Day 71 visit (end of treatment/early termination [EOT/ET]) will be performed for each subject. After Day 71, the subjects will be observed every 3 months from their first exposure to EN3835 up to a maximum of 1 year in each treated quadrant (including

both open-label and double-blind treated quadrants, if different quadrants were treated across both studies). Durability beyond Day 360 will be assessed in subjects who received active treatment in EN3835-201 and showed a composite improvement of at least 1 level on both the CR-PCSS and the Patient Reported Photonic Cellulite Severity Scale (PR-PCSS). In these subjects, the original quadrant treated in EN3835-201 will be assessed until the end of the current study, in addition to any treated quadrants occurring in the current study. Assessments of durability beyond Day 360 may also include subjects who opted not to receive additional treatments in EN3835-202.

1.2. Schedule of Study Assessments

[Table 2](#) lists the schedule of observation assessments, [Table 3](#) lists the schedule of treatment session assessments, [Table 4](#) lists the schedule of long-term durability assessments.

The schedule of observation assessments is applicable for both observation only and treated subjects in current study. For example, if subjects received treatments (ie, re-treatment, re-dosing, or a first treatment) in current study may be scheduled for observation assessments up to maximum of 1 year for each treated quadrant.

NOTE: Observation visits ([Table 2](#)) in the open-label extension study begin after completion of double-blind study (Day 71). Treatment sessions ([Table 3](#)), if elected, will begin after study drug blind is broken in study EN3835-201 while observation visits continue concurrently. Durability visits ([Table 4](#)) are for the subjects who received active treatment in EN3835-201 and scored an improvement of at least 1 level on both the CR-PCSS and the PR-PCSS at the same visit on or before Day 71 in the double-blind study EN3835-201.

Table 2: Schedule of Observation Assessments

Procedures	Screening A ^a (≥Day 71 Visit of Double-blind Study)	Visit 1 Day 90 ^b (±7 days)	Visit 2 Day 180 ^b (±7 days)	Visit 3 Day 270 ^b (±7 days)	Visit 4 End of Study/ Early Termination Day 360 ^{b,f} (±7 days)
Informed Consent	X				
Inclusion/Exclusion	X				
Digital photography		X ^c	X ^c	X ^c	X ^c
Prior/Concomitant Medications/Procedures	X	X	X	X	X
Body weight		X	X	X	X
Vital signs		X	X	X	X
Collection of samples:					
• Clinical laboratory					X
• Anti-AUX-I/anti-AUX-II antibody level					X
Subject cellulite assessments:					
• Patient Reported Photonumeric Cellulite Severity Scale (PR-PCSS)		X ^{d,e}	X ^{d,e}	X ^{d,e}	X ^{d,e}
• Subject Global Aesthetic Improvement (S-GAIS)					X ^{d,e}
• Subject satisfaction with cellulite treatment assessment					X ^{d,e}
Investigator cellulite assessments:					
• Clinician Reported Photonumeric Cellulite Severity Scale (CR-PCSS)		X ^e	X ^e	X ^e	X ^e
• Hexsel Cellulite Severity Scale (CSS)					X ^e
• Investigator Global Aesthetic Improvement (I-GAIS)					X ^e
Injection site reactions/local tolerability in assigned quadrant from EN3835-201 study		X	X	X	X
Adverse events		Monitored Throughout Study			

^a Informed consent for open-label observation assessments and optional treatment election.

^b Four (4) visits at 3-month periods begin 90 days after Day 1 of the double-blind study (EN3835-201) (ie, within 20 days \pm 4 days of completion of double-blind study).

^c Only the treated quadrant(s) is photographed. For subjects participating in observation-only visits, the quadrant treated in the double-blind study (EN3835-201) is photographed; for subjects with open-label treatment (treated with EN3835 in study EN3835-202), the treated quadrant is photographed.

^d Assessment made via viewing digital image photograph.

^e Assessment of treated quadrant(s) only.

^f For subjects treated with active EN3835 in the double-blind study and having a different quadrant treated in the open-label study, refer to [Table 4](#) for continued assessments of the double-blind treated quadrant for durability beyond Day 360. NOTE: Subject cellulite assessments must be completed before the Investigator cellulite assessments are conducted at each visit.

NOTE: Subject cellulite assessments must be completed before the Investigator cellulite assessments are conducted at each visit.

Table 3: Treatment Session Assessments

Procedures	Screening B ^a (Day -14 to -1 relative to Tx Visit 1)	Tx Visit 1 Tx Session 1 Day 1	Tx Visit 2 Tx Session 2 Day 22 (± 3 days)	Tx Visit 3 Tx Session 3 Day 43 (± 3 days)	Tx Visit 4 End of Treatment/ Early Termination Day 71 (+5 days) ^b	
Inclusion/Exclusion	X					
Digital photography	X ^c	X ^{c,d}	X ^{c,d}	X ^{c,d}	X ^c	
Medical history/EFP history including previous treatments	X ^{k,m}					
Prior/Concomitant Medications/Procedures	X ^{k,m}	X ^m	X	X	X	
Physical examination:	X					
• Body weight	X ^m		X ^e	X ^e	X	
• Height	X ^m					
Vital signs	X	X ^f	X ^f	X ^f	X	
12-lead ECG	X ^l					
Collection of samples:						
• Clinical laboratory	X ^m				X	
• Anti-AUX-I/anti-AUX-II antibody level		X ^{e,m}			X	
• Urine pregnancy testing	X	X ^e	X ^e	X ^e		
Subject cellulite assessments:						
• Patient Reported Photounumeric Cellulite Severity Scale (PR-PCSS)	X ^{g,h}		X ^{e,g,h}	X ^{e,g,h}	X ^{g,h}	
• Subject Global Aesthetic Improvement (S-GAIS)					X ^{g,h}	
• Subject satisfaction with cellulite treatment assessment					X ^{g,h}	
Investigator cellulite assessments:						
• Selection of dimples to be treated within selected quadrant		X ^e	X ^e	X ^e		
• Marking the dimples to be treated within selected quadrant		X ^e	X ^e	X ^e		
• Clinician Reported Photounumeric Cellulite Severity Scale (CR-PCSS)	X ^h		X ^{e,h}	X ^{e,h}	X ^h	
• Hexsel Cellulite Severity Scale (CSS)	X ^{h,i}				X ^h	
• Investigator Global Aesthetic Improvement (I-GAIS)					X ^h	
Confirm Eligibility	X	X ^e				
Select Quadrant	X ^j					
Study drug administration		X	X	X		
Injection site reactions/local tolerability in selected quadrant		X	X	X	X	
Adverse events			Monitored Throughout Study			

^a After the study drug blind is broken in study EN3835-201, eligible subjects may elect to receive EN3835 treatments.

^b Upon completion of treatment, subject will be followed at 3-month intervals as in [Table 2](#); if study terminates early, subject will be followed through Visit 4 (Day 71). If subject received placebo in the double-blind study (EN3835-201), she may be eligible for a total of 2 courses of treatment (a total of 6 treatment sessions) in this study.

^c All 4 quadrants are photographed at screening; at other visits, the selected quadrant only is photographed.

^d Before and after marking the dimples.

^e Before injection.

^f Up to 4 hours before injection; approximately 15 and 30 minutes after injection. Vital signs must be stable before the subject is discharged.

^g Assessment made via photograph (if treatment session, use photograph taken before marking dimples).

^h All 4 quadrants are assessed at the Screening B visit; at other visits, the selected quadrant only is assessed.

ⁱ Initial Hexsel CSS at screening must be ≤ 13 on selected quadrant.

^j To qualify for treatment, the selected quadrant must have a score of 3 or 4 (moderate or severe) in both the CR-PCSS and PR-PCSS, and a Hexsel CSS score ≤ 13 ; to qualify a quadrant that had been previously treated with EN3835 in study EN3835-201, the quadrant must have CR-PCSS and PR-PCSS scores equal to or greater than study EN3835-201 baseline scores and a Hexsel CSS score ≤ 13 .

^k Medical history and prior medications will be based on EN3835-201 eCRF; only updates and concomitant medications need to be captured at Screening B visit.

^l Do not conduct if Screening B visit date is within 12 months of obtaining an ECG during the double-blind study (EN3835-201).

^m Do not conduct on subjects eligible and opting-in for a second course of treatment in the current study (EN3835-202) if Screening B visit or Day 1 visit for second treatment course is the same day as Day 71 of the first treatment course in this study or previous study EN3835-201.

ECG=Electrocardiogram; eCRF=Electronic case report form; EFP=Edematous fibrosclerotic panniculopathy; Tx=Treatment

NOTE: Subject cellulite assessments must be completed before the Investigator cellulite assessments are conducted at each visit.

Table 4: Assessments for Durability (Beyond Day 360)

Procedures	Long-term Durability Visit 1 Day 450 ^a (±30 days)	Long-term Durability Visit 2 Day 540 ^a (±30 days)	Long-term Durability Visit 3 Day 630 ^a (±30 days)	End of Long-term Durability Study Day 720 ^a or EOS/ET (±30 days)
Informed Consent	X			
Inclusion/Exclusion	X			
Digital photography	X	X	X	X
Medical history/EFP history including previous treatments	X ^b			
Prior/Concomitant Medications/Procedures	X ^b	X	X	X
Subject cellulite assessments:				
• Patient Reported Photonumeric Cellulite Severity Scale (PR-PCSS)	X ^{c d}	X ^{c d}	X ^{c d}	X ^{c d}
Investigator cellulite assessments:				
• Clinician Reported Photonumeric Cellulite Severity Scale (CR-PCSS)	X ^d	X ^d	X ^d	X ^d
• Hexsel Cellulite Severity Scale (CSS)	X ^d	X ^d	X ^d	X ^d
Adverse events			Monitored Throughout Study	

^a Days listed reflect time from Day 1 visit in the double-blind study (EN3835-201).

^b Only updates to medical history, prior medications, and concomitant medications need to be captured at this visit.

^c Assessment made via photograph.

^d Only the quadrant treated with active EN3835 in study EN3835-201 is assessed for subjects participating in durability assessments beyond Day 360.

EFP=Edematous fibrosclerotic panniculopathy; EOS=End of study; ET=Early termination

1.3. Study Objectives

1.3.1. Primary Objective

The primary objective of this study is to assess long-term safety of EN3835 0.84 mg at scheduled intervals over 1 year (12 months) or more in all subjects with EFP who elect to enroll in this open-label trial regardless of their decision to receive treatment (re-treatment or re-dosing) of open-label EN3835 or opt to receive no treatment.

1.3.2. Secondary Objectives

The secondary objectives of this study are:

- To evaluate safety and immunogenicity of re-treating or re-dosing a subject that had previously received treatment with EN3835
- To evaluate the durability of response to EN3835 in EFP severity over the 12-month post initial dosing of EN3835 in subjects previously receiving active treatment in study EN3835-201 using the PR-PCSS and the CR-PCSS
- To evaluate the durability of response to EN3835 in EFP severity beyond 12-month post initial dosing of EN3835 in subjects previously receiving active treatment in study EN3835-201 using the PR-PCSS and the CR-PCSS
- To evaluate long-term response to EN3835 in assessments of EFP including subject satisfaction, Investigator Global Aesthetic Improvement Scale (I-GAIS), and Subject Global Aesthetic Improvement Scale (S-GAIS)
- To assess cellulite severity assessments in quadrants treated in this study with EN3835
- To evaluate immunogenicity after exposure to EN3835

1.4. Study Medication

Subjects will be administered a maximum of EN3835 0.84 mg from a total of up to 12 injections. Up to 12 injections will be administered at each treatment session to treat the selected quadrant. Each of the injections will be administered as three 0.1-mL aliquots (total injection volume per injection is 0.3 mL; total injection volume per treatment session is 3.6 mL [12 injections × 0.3 mL], see [Table 5](#) below).

Subjects will receive 3 treatment sessions (Day 1, Day 22, and Day 43) separated at least 21 days unless the chosen quadrant has no further treatable EFP dimples and the Investigator rates the quadrant a score of 0 on the CR-PCSS.

Table 5: EN3835 Administration

Dose per Each Injection ^a	Injection Volume per Each Injection	Maximum Number of Injections per Each Treatment Session	Maximum Dose (mg) per Each Treatment Session	Maximum Injection Volume (mL) per Each Treatment Session	Maximum Cumulative EFP Dose
EN3835 0.07 mg	0.3 mL	12 injections	0.84 mg (12 injections × 0.07 mg)	3.6 mL (12 injections × 0.3 mL)	2.52 mg (3 treatment sessions × 0.84 mg)

^a Each injection of EN3835 is 0.3 mL administered as three 0.1-mL aliquots.

The complete Schedule of Events is provided in Section 1.2 (Table 2, Table 3 and Table 4).

1.5. Randomization and Unblinding

This study will be conducted as an open-label investigation; no randomization and blinding of assigned treatment will occur.

1.6. Interim Analysis

No interim analysis is planned for this study.

1.7. Sample Size Justification

Approximately 350 subjects that completed the EN3835-201 study will enroll in the current study. This sample size should be adequate to determine long term safety and cellulite assessments of EN3835.

2. ANALYSIS POPULATIONS AND PHASES

The following populations will be considered in the statistical analysis of the study:

- Observation Population: The Observation population includes all subjects rolled over from study EN3835-201. The cellulite assessment evaluations and safety analyses on data collected during observation phase will be performed using this population.
- Safety Population: The Safety population will include all subjects who receive at least 1 dose of EN3835 in the current study. All safety analyses for the treatment phase will be performed using this population. For by region summaries, safety population is considered within each treatment course.
- Effectiveness Population: The Effectiveness population includes all safety subjects who have a baseline and at least 1 post-baseline assessment on both the CR-PCSS and PR-PCSS on the quadrant selected for treatment in the current study. All analysis of effectiveness for the treatment phase will be based on this population. For by region summaries, effectiveness population is considered within each treatment course.
- Durability Population: This population is defined as all active responders who have both CR-PCSS and PR-PCSS at 180 days or above. The active responders are subjects treated with EN3835 with improvements of at least 1 level on each

scale (CR-PCSS and PR-PCSS) at Day 71 visit compared to the baseline. Analysis of durability of treatment effect will be performed using this population.

- Durability Population for Double-blind Treated Subjects: This population is defined as all subjects in the durability population who showed an improvement of at least 1 level on each scale (CR-PCSS and PR-PCSS) at Day 71 visit compared to the baseline for the quadrant treated with EN3835 in double-blind study EN3835-201.
- Durability Population for Open-label Treated Subjects: This population is defined as all subjects in the durability population who showed an improvement of at least 1 level on each scale (CR-PCSS and PR-PCSS) at Day 71 visit compared to the baseline for the quadrant treated with EN3835 in the open-label study EN3835-202 study, who did not have the same quadrant treated with EN3835 in double-blind study EN3835-201. For by region summaries, this population is considered within each treatment course.

The following 2 phases will be summarized in the statistical analysis of the study:

- Observation phase: Observation phase is defined as the time period from Screening A to the first treatment date of the same quadrant in study EN3835-202 or the end of study EN3835-202 if there is no treatment received for the same quadrant in study EN3835-202. Observation phase is defined within each treated quadrant, unless the summary is for subject level only and cannot be differentiated by the treated quadrant, ie, disposition, adverse event (AE). For subject level summaries, observation phase is defined as the time period from Screening A to the first treatment date in study EN3835-202 or the end of study EN3835-202 if there is no treatment received in study EN3835-202.
- Treatment phase: Treatment phase is defined as the time period from the first treatment date of certain quadrant in study EN3835-202 to the end of study EN3835-202. Treatment phase is defined within each treated quadrant, unless the summary is for subject level only and cannot be differentiated by the treated quadrant, ie, disposition, AE. For subject level summaries, treatment phase is defined as the time period from the first treatment date to the end of study EN3835-202.

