17.2.1. Observational Population

The Observational population includes all subjects treated with EN3835 in study EN3835-201 who do not receive any treatment in the current study. The durability of a treatment effect and long-term safety analyses for subjects who receive no treatment in the EN3835-201 study will be performed using this population

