17.2.2. Safety Population

The Safety population will include all subjects who receive at least 1 dose of EN3835 in the current study or in study EN3835-201. All safety analyses will be performed using this population.

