7.4. Adverse Events

Treatment-emergent adverse events (TEAEs) is defined as any AE with onset date on or after the treatment start date in each treatment course in study EN3835-202. TEAEs are defined within each treatment course in study EN3835-202. AEs with missing or partial onset date and cannot be determined in which treatment course it occurred with its onset and end dates will be considered as TEAEs in treatment course 1. AEs with missing or partial onset date and cannot be determined in which treatment session it occurred with its onset and end dates will be considered as earliest treatment course and earliest treatment session possible.

Treatment-related adverse events are TEAEs with a relationship to study medication of possible, probable, or missing.

AEs will be coded using the Medical Dictionary for Regulatory Activities (MedDRA), Version 19.0.

Overall AE summaries for observation phase as well as overall TEAE summaries for treatment phase will be tabulated. Descriptive statistics (the number and percentage) for subjects reporting AEs, TEAEs, and Adverse Events of Special Interest (AESI) will be tabulated by system organ class (SOC) and preferred term (PT); by SOC, PT, and severity; and by SOC, PT, severity and relationship to study drug. TEAE will also be summarized by SOC, PT, and treatment course. The duration of treatment related AE descriptive statistics will be summarized within each PT under each SOC. The TEAE tables will be sorted by SOC and PT in decreasing frequency of the number of subjects in the overall column.

If there are more than 1 AE coded to the same SOC or PT for the same subject under a certain column in the summary table, the subject will be counted only once for that SOC or PT under that column. If there are more than 1 AE coded to the same PT for the same subject, the subject will be counted only once for that PT using the most severe and most related occurrence for the summarization by severity and by relationship to the study drug. If there are more than 1 AE coded to the same PT, the longest AE will be used for that PT for the duration descriptive statistics.

Serious adverse events (SAEs) and AEs leading to premature discontinuation of study drug will be summarized. Listings will be presented for subjects with AEs, SAEs, AESI, AEs leading to discontinuation, and subjects who die (if any).

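### No SAP safety population means ever exposed to EN3835, and the SAP does not promise observation-phase adverse events by parent-study arm

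*Combined protocol and SAP*

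**What the plan says.** **Protocol (Amendment 2).** Section 17.2.2 defines: "The Safety population will include all subjects who receive at least 1 dose of EN3835 in the current study or in study EN3835-201". That set serves every safety analysis. Section 17.2.1 defines: "The Observational population includes all subjects treated with EN3835 in study EN3835-201 who do not receive any treatment in the current study". Both definitions read the same in Amendment 1 and in the first protocol. Section 17.6 has adverse events (AEs) summarised by treatment group.

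**SAP section 2.** The Safety definition is narrower: "The Safety population will include all subjects who receive at least 1 dose of EN3835 in the current study". Its scope is also limited: "All safety analyses for the treatment phase will be performed using this population". The observation set is wider: "The Observation population includes all subjects rolled over from study EN3835-201", and observation-phase safety is analysed on it. For subject-level summaries such as AEs, the observation phase runs from Screening A to the first EN3835-202 dose, or to study end if there is none.

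**SAP section 7.4.** "Overall AE summaries for observation phase as well as overall TEAE summaries for treatment phase will be tabulated". A treatment-emergent AE (TEAE) needs an onset on or after the start of an EN3835-202 treatment course. Treatment-related AEs are the TEAEs whose relationship to study drug is possible, probable or missing.

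**SAP section 6.2.3.** The observation-phase cellulite endpoints are to be shown by the arm assigned in EN3835-201. Section 7 has no matching sentence for AEs.

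**SAP section 1.3.1.** The primary objective reads: "to assess long-term safety of EN3835 0.84 mg at scheduled intervals over 1 year (12 months) or more in all subjects with EFP". It covers every woman enrolled, whether or not she chooses treatment.

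**SAP section 9.** It discloses that phases and populations replace the protocol's four cohorts, and that the Observation population has been redefined. It does not list the narrower Safety definition.

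**The concern.** The long-term safety of a drug is read from the people who received it. The protocol had one set for that: everyone with a dose in either study. The SAP replaces it with two sets, and neither is that group. One leaves out women treated only in EN3835-201. The other mixes EN3835-201 active women with placebo women who have not yet had any EN3835.

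Two things are at stake. First, if the observation-phase AE table is pooled over arms, late events attributable to the drug will look rarer than they are in exposed women. Second, the women with the longest follow-up after exposure and no further dosing are those treated only in EN3835-201, and the TEAE and treatment-related definitions cannot apply to them. For a woman dosed in both studies, follow-up is cut at her first EN3835-202 dose, so no planned table counts her events from her first EN3835 exposure.

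**Working it through.** **Inputs**
- EN3835-201: 350 women randomised 1:1 (protocol section 8.3.1.4).
- Expected rollover: about 95%, giving 333 (protocol section 17.1). SAP section 1.7 gives about 350.
- AE rates and EN3835-202 treatment uptake: not given, so the values below are assumptions.

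**1. The plan's own figure.** 0.95 × 350 = 332.5, which rounds up to 333. Reproduced.

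**2. Make-up of the Observation population.** With equal rollover by arm, 333 / 2 = 166.5, or about 167 women per arm; with 350 it is 175. A placebo woman's subject-level observation phase ends at her first EN3835-202 dose, so all of that time is unexposed.

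**3. Dilution if the table is pooled.** Let w be the share of EN3835-201 active women, p_e their event percentage and p_p that of placebo women.

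Pooled = w × p_e + (1 − w) × p_p, so pooled − p_p = w × (p_e − p_p). The excess over placebo is multiplied by w.

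| Assumed p_e | Assumed p_p | Pooled, w = 0.5 | Pooled, w = 0.4 to 0.6 |
|---|---|---|---|
| 3% | 0% | 1.5% | 1.2% to 1.8% |
| 10% | 5% | 7.5% | 7.0% to 8.0% |
| 10% | 10% | 10% | 10% |

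The last column allows for uneven rollover by arm.

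**4. Treatment phase.** Every member of the SAP Safety population has received EN3835, so w = 1 and there is no dilution.

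**5. Women in the protocol's Safety population but not the SAP's.** With N = 333 and a fraction u of EN3835-201 active women treated again in EN3835-202, the number left out is 166.5 × (1 − u).

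| u | Left out |
|---|---|
| 0% | about 167 |
| 25% | about 125 |
| 50% | about 83 |
| 75% | about 42 |
| 100% | 0 |

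For example, take 50% uptake in the active arm and 75% in the placebo arm. The protocol's set is 166.5 + 0.75 × 166.5 = about 291. The SAP's set is 0.50 × 166.5 + 0.75 × 166.5 = about 208. The difference is about 83.

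**6. Definitions.** A woman treated only in EN3835-201 has no EN3835-202 course. Her AE cannot meet the TEAE definition, and treatment-related AEs are a subset of TEAEs. An event that the investigator judges related therefore falls in neither category.

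**The case against.** The strongest reply is that this is an unspecified layout, not an error. SAP section 3.1 bases denominators on column groups, and section 7.4 refers to an overall column, so other columns may be intended. If the columns follow the EN3835-201 arm, as in section 6.2.3, there is no dilution. That stands, and it makes the dilution conditional. It does not supply the missing commitment.

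A reader might go further in four ways that the documents do not support.

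- **That the 12-month safety rates are diluted.** The SAP defines no single 12-month rate, and its treatment-phase denominators are wholly exposed. Only observation-phase percentages are in question, and only if pooled.
- **That women treated only in EN3835-201 vanish from safety reporting.** They remain in the Observation population, and section 7.4 lists AEs, serious AEs (SAEs) and deaths by subject. It also calls for AE tables by relationship, which could show a related observation-phase event if run for that phase. The gap is in the Safety set and in the two defined categories.
- **That the plan overstates how firmly a rare event is ruled out.** For zero events, 1 − 0.05^(1/n) gives an upper bound of 0.90% on 333 and 1.79% on 166, but the SAP plans no confidence bound. An ever-exposed set would also exceed 166 once treated placebo women are added: about 291 in the example above, with a bound of about 1.0%.
- **That the SAP changed the protocol without saying so.** The SAP has Day 450 to Day 720 visits that Amendment 2 lacks, plans no interim analysis where Amendment 2 plans two, and restates protocol section 17.2.1 differently. It may follow a later protocol version that is not in the file.

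It is also fair to say that the primary objective covers every enrolled woman, treated or not. An all-rollover set is therefore legitimate. What is lacking is an exposed-only summary beside it.

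**Conclusion.** The point holds in limited form: should fix, with medium confidence. As written, the SAP gives no safety summary restricted to women ever exposed to EN3835 and does not commit to showing observation-phase AEs by EN3835-201 arm.

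If those events are pooled, the excess over the placebo percentage shrinks to about half, or 0.4 to 0.6 of its size if rollover is uneven. This rests on 1:1 allocation and on a true difference between arms; with equal rates there is no effect. The number of exposed women outside the SAP Safety population ranges from 0 to about 167 of 333, depending on an uptake that the documents do not give.

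The gap in the TEAE and treatment-related definitions depends on no assumption about rates. The disclosure point is firm only against the protocol text available.

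**What to change.** 1. In SAP section 7.4, state that observation-phase AEs and SAEs are tabulated by EN3835-201 treatment arm, and report relationship to study drug for the EN3835-201 active women.
2. Add an ever-exposed safety summary on the protocol's definition, "all subjects who receive at least 1 dose of EN3835 in the current study or in study EN3835-201", counting events from the first EN3835 dose. Keep the all-rollover set as an additional display, since the objective covers all enrolled women.
3. List the changed Safety definition in SAP section 9, or confirm that it matches the protocol version in force.

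The cost is SAP wording and programming, plus EN3835-201 arm, first-dose dates and AE data, which the sponsor holds. No visit or procedure changes.

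Exposure-adjusted rates by time since first dose would be a useful option but are not essential. They carry two caveats. Enrolment requires completing EN3835-201 (protocol section 11.1.1), so early time comes from women already selected for staying in. And protocol section 14.5.1 ends AE collection 30 days after the last dose, while SAP Table 2 has AEs monitored throughout; these must be reconciled before time at risk can be defined.
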